14 PHARMACOKINETIC OUTCOMES

PK sampling will include [REDACTED] sampling on Day 1 of Cycle 1 and Cycle 2 to

characterize single and multiple dose PK in subjects. The sampling scheme will be as follows:

[REDACTED]

[REDACTED]

[REDACTED]

[REDACTED]

[REDACTED]

[REDACTED]

[REDACTED]

Vodobatinib plasma concentration results will be summarized by dose. Descriptive summaries

[REDACTED]

[REDACTED] for Vodobatinib concentration will be presented for each scheduled time point. [REDACTED]

[REDACTED]

[REDACTED]

[REDACTED]

[REDACTED]

[REDACTED]

[REDACTED]

[REDACTED]

PK analysis will be performed [REDACTED]. Any missing samples due to lack of collection, loss during shipping, or other events will be reported as 'Missing' and will not be included for pharmacokinetic analysis, including descriptive statistics at nominal timepoints.

[REDACTED]

[REDACTED]

[REDACTED]

- [REDACTED]
- [REDACTED]
- [REDACTED]
- [REDACTED]
- [REDACTED]
- [REDACTED]
- [REDACTED]
- [REDACTED]
- [REDACTED]
- [REDACTED]
- [REDACTED]

- [REDACTED]
- [REDACTED]
[REDACTED]
[REDACTED]

15 SAFETY ANALYSIS STRATEGY

All analyses described in this section will be performed on the Safety Analysis set and will be presented by dose. The results will be descriptive in nature. All data will be summarized and listed.

Safety will be assessed based on exposure, adverse events (AEs/SAEs), laboratory assessments (hematology, chemistry and urinalysis), vital signs, 12-Lead electrocardiograms (ECGs) and physical examination.

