6.8.1 Primary and Secondary Target Variables

Primary Endpoints:

The primary endpoint will be:

- The MTD/RP2D as determined by the frequency of DLTs

The safety endpoint will be:

- AEs assessed based on the NCI CTCAE v4.03, ECOG performance status, vital signs, ECG, clinical laboratory values, and physical examination

Secondary Endpoints:

The secondary efficacy endpoint will be:

- Anti-leukemic response assessment following the hematological, cytogenetic and molecular assessments.

The PK endpoints will be:

- [REDACTED]
[REDACTED]
[REDACTED]

Exploratory Endpoints:

The exploratory pharmacogenomics endpoint will be:

- The BCR-ABL mutation profile at baseline and at disease progression (should it occur)

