3 STUDY DESIGN

3.1 PART B

This is an open-label, dose-ranging, single-agent, multicenter, multidose, dose escalation study initiated in subjects with Ph+ CML (Ph + CML include CML-CP, AP and BP; [without the BCR-ABL T315I mutation until sufficient plasma levels found to be active preclinically in the T315I clone are achieved]) and Ph+ ALL. Eligible subjects will be treated in [REDACTED] cycles of a once-daily self-administered Vodobatinib.

To determine the MTD and/or the RP2D, the study will initiate with an accelerated titration dose-escalation design and transition to a 3+3 design when the first subject enrolled in the initial accelerated titration dose escalation cohort develops a Grade [REDACTED] or higher adverse event (AE) that is not clearly and incontrovertibly related to the underlying disease or concomitant medications.

The initial dose escalation cohorts can enroll at least 1 and up to 3 subjects into each cohort. Subject(s) enrolled into each cohort following the accelerated design of the initial escalation steps will receive the initial dose of Vodobatinib, and continue to receive Vodobatinib at the

same dose daily (unless the subject qualifies for intra-subject escalation as described in the dose escalation schema).

If more than one subject has been entered in the accelerated titration component of the study, only the first subject will be evaluable unless the Sponsor and Investigator deem otherwise. If the first subject enrolled in this cohort does not experience Grade 3 or higher AEs or DLTs during Cycle 1 of his/her study treatment (i.e., each cycle, including Cycle 1, consists of daily Vodobatinib dosing and an observation period of [REDACTED]), the dose for the next subject(s) will be escalated to the next dose level. Enrollment into subsequent cohorts will proceed only after the current cohort has completed Cycle 1 of study treatment. When more than 1 subject is enrolled, enrollment may occur concurrently.

If this first subject enrolled in the initial accelerated titration dose escalation cohort experiences a Grade 3 or higher AE that is not clearly and incontrovertibly related to the underlying disease or concomitant medications, then that cohort and all subsequent cohorts will follow the standard 3+3 design.

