For the cohorts where the 3+3 design applies, 3 subjects will be enrolled initially. Further, if there are no Dose Limiting Toxicities (DLTs) in the first 3 subjects, dose-escalation to the next higher dose level may proceed. If 1 of the 3 subjects experiences a DLT, that dose level will be expanded to 6 subjects (3 additional subjects will be enrolled).

If 2 subjects at a given dose level experience a DLT, the MTD will have been exceeded. The next lower dose level will then be expanded to 6 subjects, or if 6 subjects have already been enrolled and no more than 1 of the 6 subjects experienced a DLT, then this lower dose level will be considered the MTD. Additional subjects may be enrolled in dose escalation cohorts for further assessment of safety and efficacy of Vodobatinib at doses that have been tolerated (i.e.: doses which have <2 DLTs in 6 enrolled subjects or <1 DLT in 3 enrolled subjects).

Once the MTD or recommended Phase 2 dose (RP2D) is established, the study initially planned to enroll up to 12 additional subjects in each of the subgroups as expansion cohorts (i.e., CML-CP, CML-AP, CML-BP, T315I CML-CP, and Ph+ ALL) using the modified toxicity probability interval design starting at the MTD or RP2D for each subset of subjects. [REDACTED]

[REDACTED]
[REDACTED] Subjects with T315I mutations will not be enrolled in any part of the study.

Subject(s) in the subgroup expansion cohorts will start at MTD or RP2D achieved in the dose escalation cohorts. Initially, three subjects will be enrolled into each of the subgroup expansion cohort and monitored for DLTs. An internal Data Monitoring Committee (iDMC) will be convened

after the 3 subjects have completed the DLT observation period. The iDMC may recommend enrolling subsequent subjects at the same dose level if escalation criteria are met (e.g. DLTs in $\leq 1/3$ subjects) depending on emerging safety-efficacy profile. The second set of up to 9 subjects will be enrolled if stopping rule is not met after review of data from first 3 subjects.

During the study conduct, the study team has decided to enroll only subjects from CML-CP subgroup in the expansion cohort and limited to the sites in India only.

Dose Escalation Schema:

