5.2 SAFETY ANALYSIS SET

The Safety analysis set will include all subjects who received at least one dose of Vodobatinib.

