6 GENERAL ASPECTS FOR STATISTICAL ANALYSIS

6.1 GENERAL CONSIDERATIONS

Continuous data will be summarized [REDACTED]. Categorical variables will be summarized [REDACTED].

For all percentage calculations, the denominator will be the number of subjects in the analysis set, unless otherwise stated. Time-to-event data will be summarized [REDACTED].

[REDACTED]

[REDACTED]

[REDACTED]

[REDACTED]

[REDACTED]

[REDACTED]

[REDACTED]

[REDACTED]

[REDACTED]

[REDACTED]

[REDACTED]

[REDACTED]

[REDACTED]

[REDACTED]

[REDACTED]

[REDACTED]

[REDACTED]

[REDACTED]

[REDACTED]

[REDACTED]

[REDACTED]

[REDACTED]

[REDACTED]

[REDACTED]

[REDACTED]

[REDACTED]

[REDACTED]

[REDACTED]

[REDACTED]

[REDACTED]

[REDACTED]

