15.2 ADVERSE EVENTS

Adverse events will be collected and recorded from the time a subject sign the informed consent to the end of study period. All AEs will be classified by primary system organ class (SOC) and preferred term (PT) according to MedDRA coding dictionary. A treatment-emergent adverse event (TEAE) is an AE that begins after the first administration of Vodobatinib or any existing AEs that worsens after then first dose of Vodobatinib. All reported AEs will be listed, but only TEAEs will be summarized in tables. The reporting period for TEAE begins from the date of first dose of Vodobatinib until 30 days after the last dose of Vodobatinib. Any AE which occurs 30 days after the last dose will be reported if it is considered related to Vodobatinib by the investigator.

An overall summary of TEAEs presenting number and percentage of subjects reporting at least one TEAE for the categories presented below:

- Subjects with at least one TEAE
- Subjects with at least one TEAE related to Vodobatinib
- Subjects with at least one serious TEAE
- Subjects with at least one serious TEAE related to Vodobatinib
- Subjects with at least one TEAE leading to premature discontinuation of Vodobatinib
- Subjects with at least one TEAE leading to death
- TEAEs by highest relationship to Vodobatinib
- TEAEs by highest severity

The following summaries will be tabulated

- TEAEs overall and by SOC and PT
- Study Vodobatinib-related TEAEs, overall and by SOC and PT
- TEAEs by maximum severity, overall and by SOC and PT
- Study Vodobatinib-related TEAEs by maximum severity, overall and by SOC and PT
- Serious TEAEs, overall and by SOC and PT
- Vodobatinib-related Serious TEAEs, overall and by SOC and PT
- CTCAE grade 3 or higher TEAEs
- Vodobatinib-related CTCAE grade 3 or higher TEAEs
- TEAEs leading to discontinuation of Vodobatinib, overall and by SOC and PT

- Vodobatinib related TEAEs leading to discontinuation of Vodobatinib, overall and by SOC and PT
- TEAEs leading to death, overall and by SOC and PT
- Vodobatinib related TEAEs leading to death, overall and by SOC and PT
- TEAE leading to dose interruption/adjustment, overall and by SOC and PT
- Vodobatinib related TEAEs leading to dose interruption/adjustment, overall and by SOC and PT
- Dose Limiting Toxicities
- Summary of CVAEs
 - Subjects with at least one CVAE
 - Subjects with at least one CVAE related to Vodobatinib
 - Subjects with at least one grade 3 or higher TEAEs

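### As visibly written, the SAP's DLT table takes everyone dosed as its denominator, so the reported DLT percentage can be understated

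*SAP*

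**What the plan says.** The Part B primary endpoint in protocol 6.8.1 is "The MTD/RP2D as determined by the frequency of DLTs".

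For the analysis, SAP section 15 sets one rule for all its tables: "All analyses described in this section will be performed on the Safety Analysis set and will be presented by dose". SAP 15.2 lists "Dose Limiting Toxicities" among those tables, with no set, denominator or layout of its own. SAP 5.2 defines the set: "The Safety analysis set will include all subjects who received at least one dose of Vodobatinib". SAP 6.1 gives the default: "For all percentage calculations, the denominator will be the number of subjects in the analysis set, unless otherwise stated".

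The analysis sets visible in SAP 5.1 to 5.4 are enrolled, safety, pharmacokinetic and efficacy. Protocol 6.8.3 has safety, efficacy and pharmacokinetic sets. Neither has a set for DLT assessment.

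The design text does depend on evaluability. For accelerated cohorts with more than one subject, SAP 3.1 says that "only the first subject will be evaluable unless the Sponsor and Investigator deem otherwise". It also keeps findings after intra-subject escalation out of the MTD. Protocol 5.2 describes past cohorts by their evaluable subjects and by completion of the DLT period. The DLT definition appears only for Part B, in protocol 6.3.1.1 and SAP 3.1. Protocol 7.8.2 nevertheless refers to DLT rates when describing the monitoring of Part C.

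**The concern.** A DLT percentage can be interpreted only if everyone in the denominator could have been counted as having a DLT and was observed long enough for one to appear. The SAP's rule admits two groups that fail this test:

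- Part C subjects treated at a dose also used in Part B. No DLT is defined for them, so they add to the denominator and cannot add to the numerator.
- Part B subjects who left during Cycle 1 for a reason other than toxicity, such as rapid progression. They appear DLT-free although the observation period was not completed. Part B has no visible replacement rule (protocol 6.3.2.5), whereas Part C has one (protocol 7.3.2.5).

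This table is the reported evidence for a primary endpoint. A percentage diluted in this way would make the dose carried into Part C look better tolerated than the evaluable data show. A reader also could not tell which subjects had been judged evaluable, since that can turn on a Sponsor and Investigator decision that the table does not record.

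**Working it through.** The documents give no DLT frequency to reproduce. DLT counts by dose and the sizes of Parts B and C are redacted. The check is therefore a reading of the rules, followed by an illustration with assumed sizes.

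**Who enters the denominator under the literal SAP rule**

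| Group | In the Safety set? | Could be counted as a DLT? | Effect on the percentage |
|---|---|---|---|
| Part B, DLT period completed or DLT occurred | Yes | Yes | None; this is the intended group |
| Part B, left Cycle 1 because of toxicity | Yes | Yes: toxicity-driven discontinuation in the 28-day period is itself a DLT (protocol 6.3.1.1) | None |
| Part B, left Cycle 1 for another reason | Yes | Not fully observed | Lowers it |
| Part C at a shared dose | Yes | No DLT defined | Lowers it |

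**Size**

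Let x be the DLTs among n evaluable Part B subjects at a dose, and m the subjects added by using the Safety set. The intended figure is x/n and the tabulated figure is x/(n + m), so the percentage shrinks by the factor n/(n + m).

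Assumed ranges: n from 6 to 18, and m from 10 to 100 Part C subjects.

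| x/n | m = 10 | m = 30 | m = 60 | m = 100 |
|---|---|---|---|---|
| 1/6 = 16.7% | 1/16 = 6.25% | 1/36 = 2.8% | 1/66 = 1.5% | 1/106 = 0.9% |
| 2/12 = 16.7% | 2/22 = 9.1% | 2/42 = 4.8% | 2/72 = 2.8% | 2/112 = 1.8% |
| 1/18 = 5.6% | 1/28 = 3.6% | 1/48 = 2.1% | 1/78 = 1.3% | 1/118 = 0.8% |

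For early leavers m is small. One such subject added to 1/6 gives 1/7 = 14.3%.

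**Accelerated cohorts**

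A qualifying AE in the first subject changes the design: "then that cohort and all subsequent cohorts will follow the standard 3+3 design". All three subjects then count, and 1/3 is the design's own figure. If the cohort stays accelerated with no DLT in its first subject, 0/1 becomes 0/3, which is 0% both ways. A DLT in a later subject raises the figure to 1/3 or 2/3. Dilution from 1/1 to 1/3 needs a first-subject DLT that does not trigger conversion, for example a low-grade toxicity that forces a dose reduction. That is possible but narrow.

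**Effect on the MTD**

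The rule is a count: "If 2 subjects at a given dose level experience a DLT, the MTD will have been exceeded". Adding subjects to a table's denominator does not change a count.

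**The case against.** The strongest reply is that nothing was decided from this table. Escalation was reviewed during Part B after Cycle 1 by the internal monitoring committee, the Sponsor and the investigators (SAP 3.1, protocol 6.3.1.1). The RP2D also rests on tolerability, activity and trough levels, and protocol 7.1 says it was established before Part C. SAP section 15 calls its results descriptive. All of this stands. A reader might infer that the MTD or RP2D itself is biased; the documents do not support that.

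A second reply is that pooling of the two Parts is read from silence. Protocol 7.3.1 and 7.8.3.2 evaluate the Part C cohorts separately for safety, and protocol 6.8.8 and 7.8.9 summarise AEs by dose cohort, adding disease cohort in Part C. The DLT entry is a bare bullet, and parts of the SAP, including section 4 and much of section 6, are redacted. This stands in part. A rule may exist in redacted text, so the point is limited to what is visible. But the visible SAP wording is a positive rule covering every section 15 table, and if the protocol intends separation, the SAP should say so.

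Two further readings go too far. One is that accelerated-cohort subjects after the first generally dilute the rate; apart from the narrow exception shown above, they do not. The other is that the 3+3 rule treats early leavers as having tolerated the dose. Later cohorts open only once the current one has completed Cycle 1, and protocol 5.2 reports evaluable subjects. The text does not say how a non-toxicity leaver is counted, which is an ambiguity to reconcile and not a demonstrated error in conduct.

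**Conclusion.** The point holds for reporting. Followed literally, the visible SAP runs the DLT table on all dosed subjects by dose, so the percentage can be understated wherever Part C shares a dose row with Part B or a Part B subject left Cycle 1 for a non-toxicity reason.

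The Part C effect could be large: from 16.7% to between 6.25% and 0.9% if 1 DLT in 6 is joined by 10 to 100 Part C subjects. The effect of a single early leaver is small. These sizes are assumptions and the actual dilution cannot be computed. The Part C effect also assumes that Part B treated subjects at the Part C dose. That is inferred from Part C being run at the RP2D, since the Part B doses are redacted.

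What is affected is the reported DLT frequency supporting the Part B primary endpoint. The MTD/RP2D decision is not.

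**What to change.** - Add a DLT-evaluable set to SAP section 5 and protocol 6.8.3: Part B subjects designated evaluable who either had a DLT in the DLT period or completed that period at the assigned dose.
- Run the DLT table on this set only, by assigned Part B dose, showing numerators and denominators. List the excluded Part B subjects with reasons, including any Sponsor and Investigator decision on evaluability.
- Reconcile the mention of DLT rates for Part C in protocol 7.8.2 with a DLT definition that exists only for Part B.
- Reconcile the passages that count enrolled subjects (protocol section 3 and SAP 3.1, on doses regarded as tolerated) with those that refer to evaluable subjects or to completion of Cycle 1 (protocol 5.2, SAP 3.1). Which counting rule should govern escalation is for the sponsor and investigators; this point does not propose one.

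The cost is SAP and protocol wording plus one analysis flag derived from data already collected. Reported DLT rates may look slightly less favourable.

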7.3 INVESTIGATIONAL PLAN

7.3.1 Overall Study Design

The study will be a multicenter open-label study of oral K0706 in subjects with Ph+ CML (CP, AP, BP) who have documented resistance or intolerance to ≥ 3 prior TKIs one of which includes ponatinib. Subjects will be grouped in the following cohorts. (Subjects with Ph+ ALL will not be included the study.)

| Cohort A | Cohort B | Cohort C |
|--|--|-------------------------------------|
| Ph+ CML: Chronic Phase (CP) cohort | Ph+ CML: Accelerated Phase (AP) cohort | Ph+ CML: Blast Phase (BP) cohort |

Note: The number of subjects contributed by a site should not exceed approximately 20% of total study population as far as possible unless approved by the Sponsor.

Each of the three cohorts represent distinct patient populations and will be evaluated separately for efficacy and safety. The cohorts can be considered as 3 separate studies enrolled through this single protocol, hence no adjustments for multiplicity are planned. Eligible subjects will be treated in [REDACTED] cycles using once-daily, oral self-administered [REDACTED] K0706 and will be evaluated for K0706 anti-CML activity (hematological, cytogenetic and molecular response). Subjects enrolled in Part C [REDACTED] will remain in the study, but will not be considered for the statistical analysis for Part C. Intra patient dose escalation is permitted only for Part C subjects enrolled at [REDACTED]. Patients enrolled in Part C at [REDACTED] can be escalated upto [REDACTED] based on investigator's assessment of subject's tolerability and response.

Adverse events (AEs) will be assessed throughout the study until 30 days after discontinuation of the study drug. AEs will be graded as per National Cancer Institute, Common Terminology Criteria for Adverse Events (NCI-CTCAE) Version 5.0. AEs will be followed to a satisfactory resolution, until it becomes stable, or until it can be explained by another known cause (i.e. concurrent condition or medication) and clinical judgment of the investigator indicates that further evaluation is not warranted. Disease progression will not be captured as an AE in this study unless it leads to death or hospitalization in which case it should be reported as SAE.

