7.4.5 Warnings and Precautions

Although the effects of similar TKIs are known, all effects of K0706 cannot be reliably predicted. The preclinical data suggest an acceptable safety margin. See the IB for details on events that could be expected.

Use of anti-clotting agents

Serious bleeding events, including fatalities have occurred in patients treated with TKIs like imatinib mesylate, dasatinib and ponatinib. The incidence of serious bleeding events was higher in patients with CML-AP and CML-BP. Cerebral hemorrhage and gastrointestinal hemorrhage were the most commonly reported serious bleeding events. Most hemorrhagic events, but not all, occurred in patients with grade 4 thrombocytopenia. Caution is indicated in patients requiring medications that inhibit platelet function or anticoagulants.

Use of Cytochrome inhibitors

Tyrosine kinase inhibitors should be used with caution when concurrently used with moderate and strong CYP3A inhibitors (such as clarithromycin, indinavir, itraconazole, ketoconazole, nefazodone, nelfinavir, ritonavir, saquinavir, telithromycin, troleandomycin, voriconazole, and grapefruit juice) and moderate or strong CYP3A inducers (such as carbamazepine, phenobarbital, phenytoin, rifabutin, rifampicin, and St. John's Wort). Sensitive substrates of CYP2C8 with a narrow therapeutic index should be avoided or used with caution in this trial (Refer to section 7.4.6.1).

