7.8.3 Subject Population for Analyses

7.8.3.1 Safety Analysis Set

The safety analysis set will include all subjects who receive at least 1 administration of IMP.

7.8.3.2 Efficacy analysis set.

The efficacy analysis set will be:

Cohort A, B and C: Include subjects who have had at least one K0706 dosing.

Each of these cohorts will be assessed separately for efficacy and safety. Efficacy analysis from subjects enrolled at [REDACTED] mg will be presented separately.

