7.8.9 Safety Data Analysis

Individual and summary blood pressures, heart rate, ECG parameters and clinical laboratory data will be presented in tabular form [REDACTED] as appropriate. The data will be summarized by dose cohort and scheduled visit. Unscheduled data will not be included in the summary tables, but will be included in the listings.

For the laboratory safety data, out of range values will be flagged in the data listings and a list of clinically significantly abnormal values will be presented.

Adverse events will be tabulated and summarized according to the current version of MedDRA. AEs will be summarized according to dose and disease cohorts.

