15.1 EXTENT OF EXPOSURE

Duration of exposure, actual cumulative dose, average daily dose, dose intensity (DI) and relative dose intensity (RDI) will be summarized descriptively by the dose. Counts and percentages of subjects who have dose reductions, interruptions and dose escalation will be summarized by dose. In addition, counts and percentage of subjects who received the assigned dose will be presented. The calculations will be performed to include both the mean and median for the parameters and their respective interquartile ranges.

[REDACTED]
[REDACTED]
[REDACTED]

Cumulative Dose:

Cumulative dose of a study treatment is defined as the total dose (mg) given during the study treatment exposure. The planned cumulative dose for a study treatment refers to the total planned dose as per the protocol up to the last date of study treatment administration. The actual cumulative dose refers to the total actual dose administered, over the duration for which the subject is on the study treatment as document in the DAR eCRF. It is the sum of the non-zero total daily doses recorded over the dosing period.

[REDACTED]
[REDACTED]
[REDACTED]

[REDACTED]	[REDACTED] [REDACTED]
------------	--------------------------

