15.3 LABORATORY EVALUATIONS

Grading of laboratory values will be assigned programmatically as per National Cancer Institute (NCI) Common Terminology Criteria for Adverse Events (CTCAE) latest version based on the observed values. CTCAE Grade 0 will be assigned for all non-missing values not graded as 1 or higher.

For laboratory tests where grades are not defined by CTCAE latest version, results will be categorized as low/normal/high based on the laboratory normal ranges. Both central and local laboratory results are used for the analysis of laboratory data. The following summaries will be generated on the safety set for hematology and biochemistry parameters by dose.

- Worst post-baseline CTCAE grade (regardless of the baseline status). Each subject will be counted only for the worst grade observed post-baseline in the on-treatment period.

The following listings will be generated separately for hematology and biochemistry parameters:

- Listing of all CTCAE grade 3 or 4 laboratory toxicities.

15.4 12-LEAD ELECTROCARDIOGRAM EVALUATIONS

The following 12-lead ECG will be obtained for each subject during the study period

- Heart Rate (bpm)
- RR interval (msec)
- QRS Interval (msec)
- PR Interval (msec)
- QT interval (msec)
- QTcF Interval (msec)
- Overall Interpretation

[REDACTED]

[REDACTED]

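### For Part C the readable SAP presents safety by dose, but the protocol requires adverse events by dose and disease cohort; with one common dose, chronic, accelerated and blast phase would be merged

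*SAP*

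**What the plan says.** **SAP.** The opening of section 15 governs all safety output: "All analyses described in this section will be performed on the Safety Analysis set and will be presented by dose". Two subsections repeat the grouping. Exposure measures (15.1) "will be summarized descriptively by the dose". For laboratory grades (15.3): "The following summaries will be generated on the safety set for hematology and biochemistry parameters by dose". The adverse event tables in 15.2 are listed by type of event and by MedDRA level, with no mention of phase or cohort.

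**Protocol, Part C.** Section 7.3.1 states: "Each of the three cohorts represent distinct patient populations and will be evaluated separately for efficacy and safety". The protocol summary makes the same statement. Section 7.8.3 repeats it after defining the analysis sets: "Each of these cohorts will be assessed separately for efficacy and safety". Section 7.8.9 then fixes the table layout. For blood pressure, heart rate, ECG and laboratory data: "The data will be summarized by dose cohort and scheduled visit". For adverse events: "AEs will be summarized according to dose and disease cohorts".

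**Protocol, Part B.** Section 6.8.8 summarizes adverse events by dose cohort and asks for no disease split.

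**The concern.** The SAP is the document from which tables are programmed. If section 15 is followed as written, Part C yields no adverse event rate for chronic, accelerated or blast phase separately. Yet the protocol describes the cohorts as distinct populations and treats them as three separate studies when it justifies having no multiplicity adjustment.

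The documents give reasons to expect safety tables to vary with phase:

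- Disease progression that leads to death or hospitalization is reported as an SAE (Protocol 7.3.1 and 7.5.3.1). Serious and fatal event tables will therefore carry leukemia progression as well as drug toxicity.
- Hematological dose-limiting toxicities in Part B are defined phase by phase in both documents.
- A platelet count at or below 100 x 10^9/L, unrelated to therapy, is itself an accelerated phase criterion (Protocol Table 7-2). SAP 15.3 tabulates the worst post-baseline grade whatever the baseline status.
- Protocol 7.4.5 says of earlier TKIs: "The incidence of serious bleeding events was higher in patients with CML-AP and CML-BP". This is class background on drugs such as imatinib, dasatinib and ponatinib, not an observation on K0706.

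If event rates do differ by phase, a merged rate describes none of the three populations. It would be too high for the lowest-risk cohort and too low for the highest-risk one.

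**Working it through.** No sample size, power or event figure is involved, so the check is a comparison of texts and a count of columns.

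**1. Part C layout, document against document.**

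| Data | Protocol, Part C | SAP, readable text | Result |
|---|---|---|---|
| Adverse events | dose and disease cohort (7.8.9) | dose (15) | direct conflict |
| Laboratory | dose cohort and visit (7.8.9); cohorts assessed separately for safety (7.3.1, 7.8.3) | dose (15, 15.3) | agrees with 7.8.9 on dose; conflicts with the general rule |
| ECG, vital signs | as for laboratory | dose (15) | as for laboratory |
| Exposure | general rule only | dose (15, 15.1) | conflicts with the general rule |

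**2. Can a split by dose separate the cohorts indirectly?** It could if the cohorts took different doses. They do not: the protocol summary gives 174 mg once daily for Part C without distinction by cohort. Protocol 7.3.1 and SAP 3.2 leave subjects enrolled in Part C at another (redacted) dose out of the Part C statistical analysis. Hence:

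- columns required by Protocol 7.8.9 = 1 dose x 3 cohorts = 3
- columns produced by SAP 15 = 1 dose = 1

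Even if the subjects enrolled at the other dose were tabulated, the SAP rule would add a dose column, not a phase column.

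**3. How many tables are touched?** SAP 15.2 lists seven kinds of TEAE table: all, by maximum severity, serious, Grade 3 or higher, leading to discontinuation, leading to death, and leading to interruption or adjustment. Each is also produced for drug-related events, so 7 x 2 = 14. Three CVAE tables and one overall TEAE summary bring this to 14 + 3 + 1 = 18. No readable line asks for any of them by cohort.

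**4. Does another SAP section supply the split?**

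- Section 7 (disposition) allows presentation by disease type, as an option.
- Section 8 (baseline) requires it, for baseline data.
- The efficacy text ahead of section 13 separates all CML from CML-CP and makes stage of CML optional, for efficacy only.

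None of these reaches safety results. They do show that the SAP names disease grouping where it intends it.

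**The case against.** The strongest reply is that the SAP nowhere says dose is the only grouping. Most of SAP 6.1, parts of 15.1 and 15.4, and a block after 15.6 are blacked out, and a general subgroup rule could sit there. That stands: the point can be made only about the readable text. It does not remove the conflict, because the readable sentence covers all analyses in the section and gives a different grouping from Protocol 7.8.9.

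Second, for laboratory, ECG and vital-sign data the specific Part C sentence in Protocol 7.8.9 names dose cohort and visit, not disease. That also stands. For those tables the case rests on the general statements in 7.3.1 and 7.8.3 and is weaker.

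Third, safety is descriptive and no formal testing is planned, so no inference is damaged. This is true, but the missing output is itself descriptive: per-cohort rates that the protocol says will be given.

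A reader might go further and infer that Part B safety tables should also be split by disease. The documents do not support that: Protocol 6.8.8 specifies dose cohort, and the SAP agrees with it. Splitting escalation cohorts that start at 1 to 3 subjects would also leave many columns nearly empty. A reader might also infer that Part B subjects, including those with Ph+ ALL, will share the Part C dose column. Part B dose levels are redacted, so this cannot be shown.

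**Conclusion.** The point holds for Part C, and it should be corrected. For adverse events the two documents give conflicting layout rules. Because the dose is common to all three cohorts, the SAP's rule yields one group where the protocol requires three. For exposure, laboratory, ECG and vital-sign data there is a conflict with the general rule only.

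The conclusion assumes that the redacted SAP text contains no cohort split for safety. It needs no assumption about event rates.

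The clinical size of any distortion cannot be stated. It is tempting to read the bleeding sentence as showing that merged K0706 rates would mislead by some known factor. The documents do not support that: the sentence concerns other TKIs and gives no rates, and the Part C cohort sizes are redacted. Any such figure would consist wholly of assumptions.

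**What to change.** Amend SAP 15, or 15.2, to say that Part C adverse event tables are presented by Cohort A, Cohort B and Cohort C within dose, with a total column. At minimum this should cover all TEAEs, drug-related, serious, Grade 3 or higher and fatal TEAEs, and CVAEs. Part B can stay by dose cohort, as in Protocol 6.8.8.

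Extending the layout to hematology and laboratory grades is advisable under Protocol 7.3.1 and 7.8.3, although the laboratory sentence in 7.8.9 does not itself demand it. If that is done, the 7.8.9 sentence should be aligned. If a redacted part of the SAP already contains the split, a cross-reference in section 15 is enough.

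The cost is one sentence and extra columns in the table shells. Cohort is assigned at screening, so no new data are needed, and no dose or clinical rule changes. The drawback is small denominators in some columns; showing counts beside percentages and keeping the total column deals with this adequately.
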